#### SECTION 1A. RESEARCH STUDY OVERVIEW

#### **Subsection 1A.1 Overview & Introduction**

This three-year study will be a mixed-method, open-label cluster randomized clinical trial to test the benefit of the adapted mindful self-compassion intervention (MSC) at improving primary (PTSD, substance use) and secondary outcomes (depression, anxiety, helplessness, loneliness) among a sample of women experiencing homelessness (WEH) with PTSD/SUD residing in a residential drug treatment site (RDTS). An exploratory aim will be to elucidate mechanisms of treatment-response and maintenance or remission of symptoms.

Phase 1 of this three-year study was completed in December 2023. In Phase 1, a Community Advisory Board (CAB) was created, with women from the RDTS as well as site staff (including clinicians and substance use counselors). The CAB and the UCLA research team jointly created a semi-structured interview guide that was used with four focus groups (total N=27) of trauma-exposed WEH living at the RDTS. The participants completed acceptability and feasibility questionnaires and provided feedback on program design and administration. These suggestions were brought to the CAB and together the study design was finalized accordingly.

Phase II of this study will begin in Winter/Spring 2024. This will be a clinical trial comparing the MSC intervention to treatment as usual (TAU).

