# Section 3 – Data analytic plan

• *Power analysis*. Sample size was estimated using G\*Power and standard guidelines for testing mediation,  with α=.05, β=.80, and the standard deviation bound at ±1.91. Effect size estimates were derived from prior research on SC interventions for PTSD, which found a small-medium effect size (Cohen's d=0.2-0.5).  Particularly since the effect of MSC to reduce PTSD symptoms is emerging research, findings have been mixed regarding effect sizes for direct and indirect effects of SC interventions on PTSD, with some studies finding large effects of reduced PTSD due to SC interventions,  and others finding medium effect sizes.  (Of note, few randomized trials have been conducted).  To account for additional covariates, the clustering design,  and Type 1 error due to multiple tests, a small-medium effect size of .3 was conservatively estimated. Sample size appropriate for mediation was derived from a percentile bootstrap method, which simulations consistently show to be the most powerful test compared to similar methods (e.g., Sobel, bias-corrected bootstrap).  This yielded a final sample size of 162. Based on the team's prior research, we conservatively estimate 80% retention over time for a target enrollment of 202, for a total of 8 cohorts of 24-26 participants (divided equally into two groups per cohort). In the

team's prior work, 82% of those screened were eligible for participation: thus, we will aim to screen 246 WEH.

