- To evaluate reductions in PTSD symptoms, first, treatment response ( $\geq$  5-point reduction in symptoms) and clinically meaningful improvement (≥ 10-point reduction in symptoms) will be calculated for both immediate and 4-month follow-up. Potential covariates (e.g., demographic indicators; type, timing and amount of trauma exposure, including history of incarceration) will be screened for inclusion (included if p<.05). Change over time will be analyzed, using data from the three time points, using a mixed-effects repeated measures approach. This will also allow for a test of fixed (e.g., treatment group) and random (e.g., cohort) effects over time and conserves power by capitalizing on the longitudinal design. Reductions in PTSD will be examined using a modified Poisson distribution with robust variance, which tends to be less biased than a logit-based approach. Reductions in symptoms (measured continuously) will also be evaluated using a Gaussian distribution. Substance use will be evaluated using the TLFB, quantified as time to first use, days of use and relapse status (abstinent [did not use], lapse [used after study intervention but did not revert to regular use], or relapse [used substances for more than one third of days]). 34,35 Group x time contrasts will be tested. Identical analytic approaches will be used to examine secondary outcomes (suicidality, depression, and anxiety).
- To test for mediation effects, AGReMA (A Guideline for Reporting Mediation Analyses of Randomized Trials and Observational Studies) will be followed. A series of longitudinal structural equation models (SEM) will examine both direct and indirect effects by which change in mediators (emotion regulation, trauma-related guilt, trauma-related shame, moral injury and craving) are associated with change in PTSD, substance use, and secondary outcomes over time. Confidence intervals for indirect effects will be obtained through percentile bootstrap. SEM has the capacity to test for bidirectional

effects between PTSD symptoms and substance use. Model fit (e.g., Root Mean Square Error of Approximation) will be compared to find hypothesized paths that best fit the data.

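### The power section says an effect of .3 covers clustering and multiple tests and gives N=162, but neither reading of .3 supports this, and no power is stated for MSC vs TAU on eight randomised cohorts

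*Combined protocol and SAP*

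**What the plan says.** The only derivation of the sample size is the Power analysis paragraph of Section 3. Subsection 2.11 repeats only the retention, enrolment and screening figures.

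- The error rates are given "with α=.05, β=.80, and the standard deviation bound at ±1.91". The .80 is evidently power, mislabelled as beta.
- Prior work is summarised as Cohen's d of 0.2 to 0.5, with some larger effects. The planning value is then justified thus: "To account for additional covariates, the clustering design" and "Type 1 error due to multiple tests, a small-medium effect size of .3 was conservatively estimated".
- The test behind the number is a mediated effect: "Sample size appropriate for mediation was derived from a percentile bootstrap method". Then: "This yielded a final sample size of 162".
- Retention of 80% takes 162 to 202 enrolled, and 82% eligibility takes 202 to 246 screened.

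Subsection 2.2 randomises whole cohorts, eight in total, and Table 2 shows four per arm. Subsection 1A.1 makes PTSD and substance use under MSC the primary question and treats mechanisms separately: "An exploratory aim will be to elucidate mechanisms of treatment-response and maintenance or remission of symptoms". The mediation paragraph of Section 3 names five mediators: "emotion regulation, trauma-related guilt, trauma-related shame, moral injury and craving".

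**The concern.** A reader is told that clustering and multiplicity have been allowed for inside the choice of .3. Nothing in the text lets the reader check this: there is no scale for .3, path value, ICC, design effect, number of tests or adjusted alpha. Planning on a smaller effect raises N, but it does not control Type 1 error, whatever scale is meant.

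The derivation shown also belongs to the exploratory aim. For MSC vs TAU the information is limited by eight randomised units, and no power or detectable difference is given. If that comparison turns out null, readers who believe clustering was covered may over-read it.

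**Working it through.** **Inputs from the documents.** Alpha .05 (two-sided assumed, since sidedness is not stated); power .80; effect .3; 162 analysable, so 81 per arm; eight cohorts, four per arm, so 162/8 = 20.25 analysed per cohort; five mediators.

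**Assumptions, not in the documents.** ICC 0 to .05; over-time correlation r of .7 or .8; cohort-level df of 8 − 2 = 6.

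**Step 1. The plan's own figures.** 162/.80 = 202.5 (202 stated) and 202/.82 = 246.3 (246 stated). Both reproduce. The 162 cannot be reproduced from .3.

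**Step 2. Reading .3 as Cohen's d**, the only metric the paragraph names. For a simple two-arm comparison of independent women, the noncentrality is d·√(n/2) = .3·√40.5 = 1.91 on 160 df, giving 47.5% power. For 80%, 176 per arm (352) are needed.

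**Step 3. Reading .3 as both mediation paths.** Percentile-bootstrap simulation (3,000 replicates, 600 resamples), one mediator, independent women:
- n=120: 80 to 82%
- n=162: about 93%

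So 162 carries a surplus of 162/120 = 1.35. As a design effect, 1 + 19.25·ICC = 1.35 gives ICC = .018, with nothing left for multiplicity. Spent instead on a stricter alpha, it buys about .0125 (79% simulated), with nothing left for clustering.

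The same paths with eight cohorts of 20 or 21, arm-to-mediator path tested on 6 df, mediator-to-outcome path within cohort, both required to be significant, same ICC in mediator and outcome:

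| ICC | 0 | .01 | .02 | .05 |
|---|---|---|---|---|
| alpha .05, one test | 84% | 79% | 74% | 58% |
| alpha .01 (.05/5: five mediators, one outcome) | 48% | 42% | 36% | not tabulated |

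Repeat runs differ by one or two points.

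**Step 4. MSC vs TAU.** Noncentrality = d / √[(2/81)·V·DE], with DE = 1 + 19.25·ICC (1, 1.19, 1.39, 1.96 at ICC 0, .01, .02, .05) and two-sided critical t of 2.447 on 6 df. V is 1 for one unadjusted follow-up, 1 − r² for one baseline-adjusted follow-up (.51 at r=.7), and (1 + r)/2 − r² for two follow-ups averaged and adjusted (.36 at r=.7, .26 at r=.8). Example: V=.36, ICC .01 gives .3/√(.0247 × .36 × 1.1925) = 2.91, hence 68%.

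| Analysis, d=.3 | ICC 0 | .01 | .02 | .05 | d detectable at 80%, ICC 0 to .05 |
|---|---|---|---|---|---|
| one follow-up, unadjusted | 36% | 31% | 28% | 21% | 0.53 to 0.74 |
| one, adjusted, r=.7 | 61% | 54% | 48% | 36% | 0.38 to 0.53 |
| two, adjusted, r=.7 | 76% | 68% | 62% | 48% | 0.32 to 0.45 |
| two, adjusted, r=.8 | 87% | 81% | 76% | 61% | 0.27 to 0.38 |

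At d=.5, one adjusted follow-up at r=.7 gives 96 / 92 / 88 / 76%.

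The adjusted rows assume that adjustment and averaging shrink between-cohort variance in the same proportion as within-cohort variance. If they do not, the 81% cell becomes 65%. With 160 individual-level df, hard to justify with eight cohorts, the two-follow-up rows at ICC .01 / .02 / .05 become 83 / 77 / 62% (r=.7) and 93 / 89 / 76% (r=.8).

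**The case against.** The best defence is that the paragraph does not claim to have inflated N. It claims to have planned on a smaller effect than some prior studies found, so the allowance is the gap between expected and planned effect. That is a fair description of the text, and the d=.5 row shows that a larger true effect would leave good power even on 6 df. The defence does not rescue the stated claim. The allowance is tied to no ICC or number of tests, and planning conservatively on effect size leaves the false-positive rate where it was.

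A second defence is that .3 may be a path value, so that 162 holds a real surplus. This also stands in part: for one test at an ICC of about .01 or less, power is close to or above 80%. The surplus still cannot fund both allowances.

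A reader might infer more: that 162 was computed with paths of about .26 and so demonstrably contains no allowance. One unclustered percentile-bootstrap test with both paths at .26 does give about 80% at n=162. But .26 is a back-calculation that appears nowhere in the documents. It is not unique either: a repeated-measures interaction with f=.10 and correlation .5 gives 163. The documents support saying that no allowance is shown, not that none was made.

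Nor do they support saying that the analysis ignores clustering or that the trial is certainly underpowered. Section 3 names cohort as a random effect and says the three-time-point model "conserves power by capitalizing on the longitudinal design". Some plausible settings exceed 80%.

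**Conclusion.** The point holds as a fault in the power statement. On neither reading of .3 does 162 deliver 80% power with clustering and multiple tests both accounted for: 48% before clustering on the Cohen's d reading, and on the path reading about 79% at ICC .01 for one test, falling below 50% at alpha .01. Power for MSC vs TAU is not stated. At d=.3 on 6 df, 2 of the 16 settings above reach 80%, both using two follow-ups with r=.8 and an ICC of .01 or less.

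The Cohen's d result needs only the stated inputs and a two-sided test. The clustered figures rest on the assumed ICC, r and 6 df, because the plan gives none of them. The enrolment and screening arithmetic is sound, and nothing here shows that N=202 must rise. The defect should be fixed before results are known, because a null MSC vs TAU result will otherwise be read against a power claim that the plan does not support.

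**What to change.** - Keep N=202.
- Correct the beta label to power .80.
- State the metric of .3 and the path values that gave 162. Unless an inflation factor is shown, say that 162 is a mediation figure before clustering.
- Replace the sentence saying that .3 accounts for clustering and Type 1 error with a calculation for MSC vs TAU: power at d=.3 and the effect detectable with 80% power, under the mixed model already in Section 3, with cohort as a random effect, four cohorts per arm and cohort-level df. Show it over a stated range of ICC (including 0) and of over-time correlation.

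The cost is SAP wording and one calculation, with no extra participants. The downside is that the stated power becomes less favourable.

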### Assessments (see detailed description above)

### Primary outcomes:

- PTSD PCL-5 (lifetime, past year):
- Substance use AUDIT DAST

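### Planning on an effect size of .3 cannot account for Type 1 error from multiple tests, and the plan defines no family of primary tests and no adjustment

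*Combined protocol and SAP*

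**What the plan says.** All references are to the combined protocol and SAP.

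- **Section 3, Power analysis.** The inputs are given as "with α=.05, β=.80, and the standard deviation bound at ±1.91". The effect size comes from prior work "which found a small-medium effect size (Cohen's d=0.2-0.5"). The plan then says that, to allow for covariates, clustering and "Type 1 error due to multiple tests, a small-medium effect size of .3 was conservatively estimated". This is its only mention of multiple testing.
- **Subsections 2.7 and 2.10.** The primary outcomes are the PCL-5 and, for substance use, "Substance use AUDIT DAST". AUDIT and DAST are each to be analysed in a continuous and a categorical form. The PCL-5 is taken for two reference events, lifetime and past year.
- **Subsection 2.6.** There are two assessments after baseline: post-intervention and 4 months.
- **Section 3, Statistical analysis.** The two PCL-5 reduction thresholds (5 and 10 points) "will be calculated for both immediate and 4-month follow-up", and continuous change is modelled as well. Substance use is evaluated here by the TLFB through three quantities (time to first use, days of use, relapse status), not by AUDIT or DAST. Group x time contrasts are to be tested, but their number, order and per-test alpha are not given. The p<.05 in this paragraph is for covariate screening.

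**The concern.** The plan presents multiplicity as dealt with, and it is not. A smaller assumed effect asks for more participants. The extra participants buy power, or could pay for a stricter alpha, but no stricter alpha is specified. When MSC has no effect, the chance of a false positive on any one test is the alpha used for that test, whatever effect the trial was planned on.

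This matters because the plan offers several routes to a significant primary result: more than one measure, two follow-ups and more than one scoring. A reader of the power section would believe that the overall error rate is protected. Without a named family and a procedure, nobody can say what that rate is, and the choice of which contrast to emphasise stays open until the data are seen.

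**Working it through.** **1. The plan's own figure.** The only relevant computed figure is the sample size: "This yielded a final sample size of 162", and then "we conservatively estimate 80% retention over time for a target enrollment of 202". The retention step agrees: 162/0.80 = 202.5.

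The 162 does not follow from d=.3 in a two-group comparison. With two-sided alpha .05 and power .80 (reading the printed β as power), n per arm = 2 x (1.960 + 0.842)² / 0.3² = 174.4, so 175 per arm or 350 in all. The plan attributes 162 to another route: "Sample size appropriate for mediation was derived from a percentile bootstrap method". It does not give the mediation path sizes, so the mismatch is not proof of an error, and nothing below depends on it.

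**2. Does the planning effect enter the error rate?** For k independent tests, each at level a, familywise error = 1 - (1 - a)^k. The planning effect d is not in the formula. For k=6 and a=.05 the result is 26.5% whether the trial was planned on d=.2, .3 or .5.

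**3. Size, if each primary test is run at .05.** The plan does not fix k, so three counts are shown, first assuming independence:

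- k=3 (PCL-5, AUDIT, DAST, one joint group x time test each): 1 - .95³ = 14.3%.
- k=4 (PTSD once, plus the three TLFB quantities once each): 1 - .95⁴ = 18.5%.
- k=6 (three measures at two follow-ups): 1 - .95⁶ = 26.5%.

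**4. Six correlated tests.** The documents give no correlations, so these are assumed: .2-.5 between measures and .5-.7 between times. Six two-sided z-tests were simulated under the null. The correlation between different measures at different times was set either to the product of the two values or to the between-measure value.

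- Between measures .2, between times .5: about 24%.
- .2 and .7: about 22-23%.
- .5 and .5: about 21-22%.
- .5 and .7: about 20%.

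The range is therefore about 20-24%.

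**5. What control would cost in power.** Inputs: 81 per arm (162/2), two-sided tests, clustering ignored, noncentral t with 160 degrees of freedom and noncentrality d x √(81/2) = 6.364d. With three tests, the first Holm step uses .05/3 = .0167.

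- d=.3 (noncentrality 1.91): power 48% at .05 and 31% at .0167.
- d=.44 (noncentrality 2.80): power 79% at .05 and 65% at .0167. The value .44 is not in the plan. It is the effect for which 162 gives about 80% power in a two-group comparison: (1.960 + 0.842) x √(2/81) = .440.

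**The case against.** The best defence is that the plan never says how many confirmatory tests there are, or that each is run at .05. Alpha appears only as a power input. The main analysis is one mixed-effects model over three time points, which could give a single joint group x time test per measure. All of that stands, and it limits what can be said about size.

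Four stronger readings are tempting, and the documents do not support them.

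- **That the plan tests three measures at two follow-ups, each at .05.** This is an inference. The six-test family is one possible count. The analysis paragraph assigns AUDIT and DAST no test and uses the TLFB instead, and the statement about both follow-ups concerns only the PCL-5 thresholds.
- **That a positive result on any one measure counts as success.** No success rule is stated. The gap is that the family and the decision rule are both undefined.
- **That familywise error reaches 46%.** That is 1 - .95¹² for twelve independent tests. Continuous and categorical scorings of the same instrument come from the same data and are strongly dependent, so 46% is at most a ceiling.
- **That the correlated six-test figure is known closely.** It rests on assumed correlations.

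It can also be said that Holm is one choice among several. That is true: a fixed hierarchy or a single primary contrast would also control the error. None of this rescues the claim itself, because no reading of the plan lets a planning effect size change a rejection threshold.

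**Conclusion.** The claim is wrong as written: planning on .3 affects sample size and power only, and nothing else in the plan controls Type 1 error across the primary tests. This conclusion needs no assumption.

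The size of the inflation is conditional. It assumes that each primary test is run at two-sided .05, and that each test holds that level once clustering by cohort is handled. Familywise error is then about 14% to 26.5% for three to six independent tests, roughly three to five times nominal. For six tests under the assumed correlations it is about 20-24%. The documents do not support a single figure, because they do not define the family.

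**What to change.** 1. Delete the statement that the effect size of .3 accounts for Type 1 error.
2. Reconcile the substance-use primary measure: AUDIT and DAST in Subsections 2.7 and 2.10, TLFB in Section 3. The family cannot be fixed until this is settled. If the TLFB is kept, say which of its three quantities is primary.
3. Before outcome data are examined, name one primary group x time contrast per primary measure, at one named follow-up, with the scoring (and for the PCL-5 the reference event) stated.
4. Test these contrasts by Holm's procedure at two-sided .05 overall.
5. Report the other scorings and the other time point as supportive, without a significance claim.

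**Cost.** No visit, instrument or recruitment target has to change, and the text is a few sentences. The real cost is power. With three tests, single-test power at the first Holm step falls from 48% to 31% at the plan's d=.3, or from 79% to 65% at d=.44. Clustering is ignored in these figures, so they are optimistic. The power statement should report this. If the loss is unacceptable, a single primary contrast named in advance would keep the full .05 for that contrast.

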- Statistical analysis. Initial analysis will include descriptive statistics. Data will be screened for outliers and deviations from normality; results will be considered in subsequent analyses. Patterns of missing data will be examined using logistic regression (0=missing; 1=complete) and will be reported in results. Based on prior research, very little missing data on key independent or dependent variables is expected. Any missing data on independent variables or continuous dependent variables will be imputed using multiple imputation and related methods. Although cohorts should be comparable in terms of demographics (e.g., age, ethnicity) and other risk factors (e.g., type of drug use, history of recidivism), propensity score methods and/or multilevel analyses (with cohort/cluster as a random effect) will be utilized to account for these or any other covariates statistically different between cohorts at baseline. Reliability for computed scores will be assessed using Cronbach's alpha. Next, a series of t-tests and chi-squares will examine differences between groups (MSC vs. TAU). Then, for each dependent variable of interest, key predictors and covariates will be examined using a series of t-tests, chi-squares, and ordinary least squares (for continuous outcomes) and logistic (for dichotomous outcomes) bivariate regression models. Type, timing and amount of trauma exposure will be examined as covariates, given their link with PTSD incidence, severity,  substance use,  and distress.

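### Eight cohorts are randomised, but Section 3 neither requires the MSC–TAU efficacy tests to account for cohort nor names a method suited to eight clusters

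*Combined protocol and SAP*

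**What the plan says.** Section 6 (Basic Definitions), Subsection 2.1 and Subsection 2.2 all make cohort the unit of allocation. Table 2 shows eight cohorts alternating between MSC and TAU, four of each.

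The Statistical analysis part of Section 3 refers to cohort in two places:

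- **Baseline differences.** It offers "propensity score methods and/or multilevel analyses (with cohort/cluster as a random effect"), and says these "will be utilized to account for these or any other covariates statistically different between cohorts at baseline".
- **Longitudinal model.** Of the mixed-effects repeated-measures approach it says "This will also allow for a test of fixed (e.g., treatment group) and random (e.g., cohort) effects over time".

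The other between-arm analyses do not mention cohort:

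- "Reductions in PTSD will be examined using a modified Poisson distribution with robust variance"
- "Group x time contrasts will be tested"
- "Substance use will be evaluated using the TLFB, quantified as time to first use, days of use and relapse status"
- "Confidence intervals for indirect effects will be obtained through percentile bootstrap"
- "a series of t-tests and chi-squares will examine differences between groups (MSC vs. TAU")

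Secondary outcomes follow the same approaches. The Power analysis part of Section 3 says the effect size of .3 was chosen partly to allow for the clustered design. It gives no ICC, design effect or degrees of freedom.

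**The concern.** With four cohorts against four, the evidence on an arm difference has 8 − 2 = 6 between-cohort degrees of freedom, however many women are enrolled. A test that counts women as independent, or applies large-sample theory to eight clusters, can take a chance difference between cohorts for an MSC effect.

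The wording permits such tests. Propensity scores alone would satisfy the and/or, and they do not correct a standard error for cohort randomisation. If baseline covariates look balanced, nothing triggers the adjustment, although the need for it comes from the design and not from imbalance. A robust variance could be computed on women or on cohorts. PTSD and substance use are the primary outcomes, and the choice between readings could be made after the data are seen.

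**Working it through.** **Inputs from the plan.** 8 cohorts, 4 per arm; 162 analysed; 202 enrolled; α = .05 (taken as two-sided); effect size .3.

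**The plan's own figures.** 162/0.80 = 202.5, which agrees with 202 enrolled; 202/8 = 25.25 enrolled per cohort; 162/8 = 20.25 analysed per cohort. The 162 comes from a mediation method whose path sizes are not given, so it cannot be reproduced. That does not show it to be wrong, and nothing below depends on how it was derived.

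**Assumptions.** 20 women analysed per cohort, no true effect, nominal 5%. ICC and cohort-by-time variance are assumed ranges.

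**1. Cohort left out, one time point.** The true variance of the arm difference is 1 + 19·ICC times the variance assumed. Type I error = 2·P(Z > 1.96/√(1 + 19·ICC)).

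| ICC | 1 + 19·ICC | Type I error |
|---|---|---|
| 0 | 1.00 | 5.0% |
| .01 | 1.19 | 7.2% |
| .02 | 1.38 | 9.5% |
| .05 | 1.95 | 16.0% |

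**2. Group × time, baseline to 4 months.** Simulation with three time points and total variance 1: cohort .05, woman .45, cohort-by-time v, remainder residual. A woman's change has variance 2v + 2(.5 − v) = 1, so the ICC of the change score is 2v. Values of v of 1% and 2% of total therefore mean change-score ICCs of .02 and .04, and should not be compared with the same labels in step 1. The step 1 formula at .02 and .04 gives 9.5% and 14.0%, in line with the simulated first row below.

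| Analysis | v = 0 | v = 1% | v = 2% |
|---|---|---|---|
| No cohort-by-time term | 5.1% | 9.6% | 14.4% |
| With the term, Wald z | 4.1% | 5.8% | 6.9% |
| With the term, Satterthwaite df | 3.5% | 4.4% | 5.0% |
| Cohort-mean change, t on 6 df | 5.0–5.2% | 5.0–5.2% | 5.0–5.2% |

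These rows take cohort effects as independent over time. If cohorts instead shift and stay shifted after baseline, or drift steadily, the Satterthwaite model gives 5.3–7.4% at v of 1–2% and about 8.5–10.6% at v = 5%. Cohort-mean change stays at about 5%.

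**3. Responder outcomes, modified Poisson.** Change dichotomised at a rate of .3 or .5, same values of v.

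- Robust variance on women: 4.6–4.7%, 7.0–7.6% and 9.4–10.4% at v = 0, 1% and 2%.
- Robust variance on the 8 cohorts, uncorrected, with z: about 13–14% at every value, including 0. With four cohorts per arm the uncorrected variance is about 3/4 of what it should be, so the effective cut-off is 1.96·√(3/4) = 1.70 on a t scale with 6 df, and 2·P(t₆ > 1.70) is about 14%.
- The same variance multiplied by 4/3, with t on 6 df: 4.6–4.9%.

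**4. Cost in power.** The critical value on 6 df is 2.447, and 2.447/1.960 = 1.25. For d = 0.3 with 81 per arm, SE = √(2/81 × (1 + 19.25·ICC)), and power comes from the noncentral t on 6 df.

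| ICC | SE | 0.3/SE | Power |
|---|---|---|---|
| 0 | .157 | 1.91 | 36% |
| .01 | .172 | 1.75 | 31% |
| .02 | .185 | 1.62 | 28% |
| .05 | .220 | 1.36 | 21% |

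These figures use no baseline adjustment. Since the plan says .3 already allows for clustering, the rows above ICC 0 may count it twice.

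**The case against.** The plan is aware of clustering. It cites a source on cluster-randomised data, names a cohort random effect twice, and says the effect size allows for the design. A reader might infer that clustering is ignored; the text does not support that. The phrase about random effects over time can fairly be read as including a cohort-by-time effect. On that reading even a plain Wald test gives only 5.8–6.9% at v of 1–2%, so the 9.6% and 14.4% belong to the least favourable reading of that model. What stands is that cohort is given as an example, the cohort-by-time term is not stated clearly, and no degrees of freedom are named. The effect-size allowance bears on planned sample size and cannot correct a standard error at analysis.

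All women come from one site, so the ICC may be near zero. That is possible, but Subsection 1A.4 shows cohorts running one after another, and MSC is delivered in groups, so zero cannot be assumed. An uncorrected cohort-level sandwich would fail even at zero.

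Three further inferences go too far:

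- **The t-tests and chi-squares as the efficacy analysis.** They read as preliminary and need only a label.
- **The bootstrap intervals as confirmatory.** Subsections 1A.1 and 2.1 already present mechanisms as exploratory.
- **A specific faulty test for time to first use or relapse status.** The plan names no such test. The TLFB is also missing from the listed measures, where AUDIT and DAST are the substance-use instruments, so the remedy must cover AUDIT and DAST.

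**Conclusion.** The concern holds. Section 3 ties one of its two references to cohort to baseline imbalance and makes the other an example. It leaves the clustering unit of the binary analysis open and names no method suited to eight clusters. Under readings the text permits, type I error for a primary outcome ranges from about 5% to about 14% across ICC 0 to .02, and reaches 16% at ICC .05 if cohort is left out altogether.

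These rates rest on assumed ICCs, equal cohorts of 20 and no true effect. They show what the wording allows and do not predict this trial's error rate. A reader might also infer that a mixed model with Satterthwaite degrees of freedom settles the matter. It does so only if cohort effects are independent over time, which the documents do not establish. Because the primary outcomes are affected and the choice cannot be prespecified once results are known, this should be settled before analysis.

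**What to change.** 1. Keep the sentence on baseline covariates and add that every MSC–TAU efficacy comparison accounts for cohort, whatever the baseline balance.
2. For continuous outcomes (PCL-5, AUDIT and DAST scores, and the secondary outcomes), make the primary test a comparison of cohort-mean changes with t on 6 df. The planned mixed model, with cohort and cohort-by-time random effects and Kenward-Roger or Satterthwaite df, can stay as supportive, with a note that it can exceed 5% if cohort shifts persist.
3. For binary outcomes (PTSD response, AUDIT and DAST yes/no), use modified Poisson clustered on cohort, with a small-sample-corrected variance and t on 6 df.
4. For any other substance-use outcome that is kept, use cohort-level summaries on 6 df.
5. Label the between-arm t-tests and chi-squares descriptive, and the mediation intervals exploratory.

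The cost is SAP wording and a little more analysis, with no change to trial conduct. Intervals widen because the critical value is 1.25 times the normal one, and the SAP should report the resulting power openly over a stated ICC range.
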